9.2.4 Representativeness

The study cohort will include 98% of all newly diagnosed PCa patients in Sweden between 2007-2016 (8). PCBaSe contains information from multiple national health care registries such as The Patient Registry, The Prescribed Drug Registry, The Cause of Death Registry, The Registry of the Total Population and Population Changes, The Registries of Immigration and Emigration and The Longitudinal database on socioeconomic factors (LISA) with data on educational level, marital status, and income.

Included in the full dataset (starting from 1998) are PCa-free men selected from the general population of Sweden for every PCa incident case (in the ratio 1 PCa patient : 5 PCa-free men) who were frequency-matched on birth year and county of residence. To date, over 180,000 incident cases of PCa, together with 900,000 PCa-free men are included in the PCBaSe. Since all PCa and non-PCa patients have the same source of information on their clinical and demographic characteristics, comparisons can be made with consideration of these baseline characteristics between the populations.

This study consisting of all men with PCa and men without PCa in Sweden observed during 2007-2016 is clearly representative of treatment patterns and occurrences of outcomes of interest in Sweden during period of time.

9.3 Variables

Baseline is defined as:

- in men with PCa: a date of an incident PCa
- in PCa-free men: a date of selection of PCa-free men (who are alive) into the database corresponding to the date of diagnosis for the index case

Index date is defined as:

- in men with PCa:
 - a date of a first cancer-related VTE event that is a VTE event related to the diagnosis of PCa (to define the relatedness, different time-frames will be specified and applied);
- in PCa-free men:
 - a date of selection into the database for defining a first recorded VTE event.

9.3.1 Characteristics of PCa and (where possible) PCa-free men:

- Age at PCa diagnosis
- Age at VTE
- Charlson Comorbidity Index (CCI) based on discharge diagnosis (including variables included into CCI)
- Specific events at baseline (that occurred prior and at the baseline) define by ICD codes for:
 - intracranial bleeding
 - gastrointestinal bleeding
 - urogenital bleeding
 - ischaemic heart disease
 - myocardial infarction

- heart failure
- stroke (ischaemic and haemorrhagic)
- transient ischaemic attack
- atrial fibrillation
- renal impairment
- renal failure
- depression
- hypertension
- hyperlipidaemia
- diabetes
- asthma
- COPD
- other cancers than PCa
- previous VTE events
- Co-medications at baseline (120 before the index event) and during follow-up (from index date)
 - Antiplatelets
 - Proton pump inhibitors
 - NSAIDs
 - SSRIs
 - Oral steroids
 - Antibiotics
 - Lipid-lowering medications
- PCa/specific parameters:
 - County
 - Hospital type (university, non-university)
 - Clinical TNM staging
 - PSA (at time of PCa diagnosis)
 - PCa risk categories (defined at diagnosis according to a modification of the National Comprehensive Cancer Network Guideline):
 - a. Low-risk: T1-2, Gleason score of 2–6 and PSA < 10 n/ml
 - b. Intermediate-risk: T1-2, Gleason score 7 and/or PSA 10–20 ng/ml
 - c. High-risk: T3 and/or Gleason score 8–10 and/or PSA 20–50 ng/ml

- d. Regionally metastatic T4 and/or N1 and/or PSA 50–100 ng/ml
 - e. Distant Metastatic disease: or M1 and/or PSA > 100 ng/ml; however PSA cutoff to be discussed
- Anti-cancer therapies that are delivered by a filled out-patient prescription

9.3.2 For patients in the VTE sub-population:

The outcome of interest is therapy with anticoagulants dispensed from pharmacies (no information is available on drugs delivered in- hospital), hence the analysis focuses on anticoagulant therapies for which an out-patient prescription has been filled, i.e. long-term therapy. A full list of the treatments with their relative ATC codes is found in Annex 3. The anticoagulation treatments that will be assessed include:

1. LMWH (after hospital discharge, long-term use)
2. VKAs
3. NOACs

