8.1 Primary objective

Among all men with PCa:

- To describe socio-demographic and clinical characteristics at the date of an incident PCa diagnosis.
- To estimate the occurrence of cancer-related VTE.
- To describe the cancer therapies in PCa at the initial time after diagnosis.

Among men with PCa and a first cancer-related VTE event:

- To characterize the long-term anticoagulation treatment including choice of drug and duration of treatment.
- To estimate the occurrence of recurrent VTE events by long-term anticoagulation treatment (LMWH, VKA or NOAC) and its estimated duration (up 3 months, 3-6 months, more than 6 months).
- To determine the time between a first cancer-related and a recurrent VTE event.
- To estimate the incidence rates of post-VTE bleeding events leading to hospitalization, and mortality by anticoagulation treatment.

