8.2 Secondary objectives

Among PCa-free men from the general population:

[figure not shown]
- To describe socio- demographic and clinical characteristics at the time of inclusion into the database.
- To estimate the occurrence of VTE events.

9. Research methods

Overview of study methodology and the process through which the study cohort will be selected is outlined in Figure 1.

Figure 1. Overview of study methodology

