9.5 Data sources

The National Prostate Cancer Register (NPCR) of Sweden captures 98% of all newly diagnosed prostate cancer cases since 1998 (8). By use of the unique Swedish Person Identity Number (PIN), the NPCR has been linked with a number of other health care registries to create PCBaSe. These include the National Cancer Registry, the National Patient Registry (with hospital and outpatient hospital clinic diagnoses), the Cause of Death Registry, the Prescribed Drug Registry with dispensed prescriptions since July 2005, and the Swedish longitudinal integration database for health insurance and labour market studies (LISA), which is a socioeconomic database with information on the educational level, income, and marital status of patients (8).

PCBaSe contains more than 180,000 Pca cases diagnosed between 1998 to 2016. The linkage of registries means PCBaSe contains comprehensive data on tumour characteristics, patients demographic, clinical and socioeconomic characteristics as well as treatment delivered or decided upon up to six months after date of diagnosis. In addition, there over 900,000 Pca-free control men (five for each PCa case matched on birth year and county of residence) derived from the general population of men in Sweden.

From PCBaSe, it is possible to extract data on the patients' dispensed drug prescriptions for anticoagulants and partially for anti-cancer therapies (since July 2005 when the Prescribed Drug Registry started). We are also able to use the in- and outpatients registries to detect any diagnosis of VTE events experienced by the patients (defined as pulmonary embolism or deep vein thrombosis). The ATC codes for the anticoagulant and anti-cancer drugs, as well as the ICD-10 codes for the VTE diagnosis are described in annex 3.

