9.8 Data analysis

Descriptive statistics will be used to define the socio-demographic and clinical characteristics (including main types of cancer therapies) of all PCa patients at the time of PCa diagnosis (Objective 1 and 3) and PCa-free men at the time of inclusion in PCBaSe (Objective 8) and include variables of interest listed above.

All categorical variables will presented by counts and proportions and continuous variables by mean, standard deviation, range, median, and first and third quartiles.

The occurrence will be estimated by calculating an incidence rate (accompanied by 95% CI) of cancer-related VTE events, split into PE and DVT events, in men with PCa (Objective 2) and in PCa-free men (Objective 10). The incidence rate is defined as the number of events of interest divided by the total number of person-years at risk. In men with PCa, the person-time at risk will be calculated from date of incident PCa diagnosis up until an outcome of interest, death or end of follow-up, whichever came first. The occurrence will be also described by Kaplan-Meier curves in different strata within different time-periods.

The AC treatment received by the PCa patients after a first cancer-related VTE event on an out-patient long-term basis will be reported by type of anticoagulation (LMWH, VKAs and NOACs) and its estimated duration (from the time-point of a hospital discharge up to 3 months, 3-6 months, more than 6 months) (Objective 4).

Time at risk for Objectives 5, 6 and 7 (recurrent VTE, bleeding leading to hospitalisation or death) will be calculated from first cancer-related VTE (the time-frame of defining cancer-relatedness will be specified later) for each events of interest up until event, death or end of follow-up.

The 95% CI for the incidence rate will be calculated using the Poisson distribution.

Incidence rates of recurrent VTE, bleedings and death will be calculated by the type and duration of AC treatment (stratification variables); however no comparative analysis of outcomes in three sub-groups of AC treatments, is planned.

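### Six comorbidities often managed outside hospital are defined by hospital ICD codes alone, so their baseline prevalences under Objectives 1 and 8 are likely to be understated

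*Protocol*

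**What the plan says.** Section 9.3.1 names 19 conditions under the line "Specific events at baseline (that occurred prior and at the baseline) define by ICD codes for". Six of them are at issue here: depression, hypertension, hyperlipidaemia, diabetes, asthma and COPD. The same section gives the "Charlson Comorbidity Index (CCI) based on discharge diagnosis (including variables included into CCI".

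For diagnoses of this kind, section 9.5 describes "the National Patient Registry (with hospital and outpatient hospital clinic diagnoses"). It also lists "the Prescribed Drug Registry with dispensed prescriptions since July 2005". No primary-care register is named among the linked sources in sections 7, 9.2.4 or 9.5.

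Dispensing data enter the baseline description only as a separate list: "Co-medications at baseline (120 before the index event) and during follow-up (from index date"). That list has SSRIs and lipid-lowering drugs. It has no antihypertensive, glucose-lowering or inhaled airway drugs, and no drug is used to define a condition.

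Objective 1 (primary) is "To describe socio-demographic and clinical characteristics at the date of an incident PCa diagnosis". Objective 8 (secondary) is "To describe socio- demographic and clinical characteristics at the time of inclusion into the database". Section 9.8 states "All categorical variables will presented by counts and proportions", so for each condition the reported result is a prevalence.

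**The concern.** Under these rules a man has one of the six conditions only if a hospital or hospital clinic recorded the code. These conditions can be managed entirely outside hospital, and men managed that way fall into the unaffected group. The tables would then present hospital-coded disease as if it were the clinical characteristic the objectives set out to describe.

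Section 9.10 covers in-hospital drugs, height, weight and lifestyle, and adherence. It does not mention under-recorded comorbidity, although item 12.1.2 of the checklist in Annex 2 says the impact of information bias is discussed. With cohorts this large the sampling error is very small, so a reader could take the figures as accurate when they are only precise.

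At stake are six rows in each of two descriptive tables, one of which serves a primary objective.

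**Working it through.** **1. Is there any other route into the data?** The sources in section 9.5, taken in turn:
- National Prostate Cancer Register and National Cancer Registry: cancer data, not these six conditions.
- National Patient Registry: ICD codes from hospitals and hospital clinics.
- Cause of Death Registry: does not describe living men at baseline.
- LISA: education, income and marital status.
- Prescribed Drug Registry: dispensings, which the protocol does not use to define any condition.

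The Charlson index adds no non-hospital source, because it is built from discharge diagnoses.

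**2. Do the planned co-medications fill the gap?** Only SSRIs and lipid-lowering drugs bear on the six conditions. Their window ends at the index event (the number 120 has no unit). Section 9.3 defines the index date in men with PCa as the first cancer-related VTE, not the PCa diagnosis, so these data do not describe the Objective 1 population at baseline. In PCa-free men the index date is the selection date, so there the window does fall at baseline.

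**3. Could the drug register serve?** From July 2005 to January 2007 is 18 months. Every man included from 2007 therefore has at least 18 months of dispensing history, which is enough for a 12-month window.

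**4. Size, for illustration only.** The protocol gives no prevalence or capture figure for these conditions, so there is no stated figure to reproduce. The interval formula used below, p ± 1.96 × √(p(1 − p)/98 000), reproduces every limit in the study-size table of section 9.6 to within 0.01 point. For example, 30% gives 29.71 to 30.29.

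Formulas, with specificity taken as 1:
- reported prevalence = true prevalence × capture
- shortfall = true prevalence × (1 − capture)
- half-width = 1.96 × √(reported × (1 − reported)/98 000)

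True prevalence and capture are assumptions.

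| True prevalence | Capture | Reported | Shortfall (points) | 95% half-width (points) |
|---|---|---|---|---|
| 5% | 0.9 | 4.5% | 0.5 | 0.13 |
| 5% | 0.3 | 1.5% | 3.5 | 0.08 |
| 20% | 0.5 | 10.0% | 10.0 | 0.19 |
| 50% | 0.9 | 45.0% | 5.0 | 0.31 |
| 50% | 0.3 | 15.0% | 35.0 | 0.22 |

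The largest possible half-width is 1.96 × √(0.25/98 000) = 0.31 points. Over the assumed range the shortfall runs from about 4 times its own half-width (5%, 0.9) to about 157 times (50%, 0.3).

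**The case against.** The strongest case on the other side has five parts.

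- **The loss is inferred.** No sentence says where these conditions are managed or how completely they are coded, and the source lists are worded as open-ended. This stands as a limit on certainty: understatement is likely, not demonstrated. It does not remove the point, because the protocol names no source that would catch these men.
- **The size is assumption only.** This stands. A reader might infer that errors of tens of points are established. The documents give no prevalence or capture for any of the six, and the mildest assumed case is half a point.
- **The reach is narrow.** This stands. A reader might infer that Objectives 1 and 8 as a whole are compromised. Six of 19 coded conditions are involved, and the objectives also cover age, socio-demographic data, tumour characteristics and more. Section 9.8 plans incidence rates and Kaplan-Meier curves with no adjustment for these variables, so the VTE, bleeding and mortality rates do not depend on them.
- **Bias between cohorts is not shown.** This stands. Section 9.2.4 says both groups share the same sources and can be compared on baseline characteristics. Men being worked up for PCa may have more hospital contact and so more recorded codes, but nothing in the protocol shows it. Nor does the protocol support the inference that one table would visibly contradict itself, with more men on lipid-lowering drugs than with hyperlipidaemia. In men with PCa the two are measured at different dates; the contrast could arise only in PCa-free men.
- **Dispensing definitions have errors of their own.** They find only drug-treated men, may not separate asthma from COPD, and can over-count where a drug has several indications. This is why both figures should be shown, not one substituted for the other.

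It could also be said that the detail belongs in a statistical analysis plan. Code lists and windows may well sit there, and Annex 3 gives no codes for the six. But the protocol has already fixed the instrument as ICD codes, and a plan that added dispensings would depart from section 9.3.1.

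**Conclusion.** The point holds within those limits. Followed as written, sections 9.3.1 and 9.5 count men managed wholly outside hospital as free of the six conditions, and section 9.10 does not say so. The six prevalences in each cohort are likely to be too low by an amount the documents do not allow one to compute; the 0.5 to 35 point range rests entirely on the assumed prevalence and capture and on perfect specificity. What does not depend on the exact values is that the large sample gives no protection, since sampling error cannot exceed 0.31 points in 98 000 men. The change should be made because it is cheap and bears on a primary descriptive objective.

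**What to change.** In section 9.3.1, for both cohorts, report two figures:

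- **(a) ICD code only**, with the rows labelled as hospital-recorded diagnosis and asthma and COPD kept separate.
- **(b) ICD code, or at least one dispensing** of a pre-listed ATC group in the Prescribed Drug Registry in a fixed window before baseline, for example 12 months. Baseline here means the PCa diagnosis date or the selection date, not the VTE index date. Asthma and COPD are combined in (b).

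In section 9.10, state that (a) misses men managed outside hospital, and that (b) captures only drug-treated men and loses some specificity where a drug has more than one indication.

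The cost is a short ATC list that goes beyond the current co-medication groups (antihypertensive, glucose-lowering and airway drugs would have to be added) and one further derivation for each row in (b), from a register that is already linked. The downside is the modest loss of specificity in (b), which stays visible because (a) is shown beside it.

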9.3.3 Outcomes of interest

In men with PCa:

1. DVT or PE
2. Bleeding events leading to hospitalisation
3. Mortality

In PCa-free men:

4. DVT or PE

9.4 Follow up

9.4.1 Exposure to anticoagulants

The exposure to AC treatment will be defined in two ways:

- the first is by following the patients until the end of the follow-up time, regardless if they are still on the drug or not.
- the second way is to follow up the patients until the filled prescription for each respective drug expires (“on/treatment”).

A grace period of 90 days will be used to define a new prescription of anticoagulant. The duration of a prescription will be derived from the median number of days between consecutive respective prescriptions after the grace period has passed.

The treatment exposure can then be used to study the switching of treatments and the discontinuation of treatments.

A start date will be defined as the date of the dispensed prescription for patients receiving anticoagulation.

Patients will be censored at earliest date of:

- Time of first occurrence of a recurrent VTE event or a bleeding event (major bleeding event i.e. intracranial, gastrointestinal, urogenital bleeding, or other bleeding leading to hospitalisation) or death
 - Patients will be followed until occurrence of one of the above mentioned outcomes of interest; similarly, the analysis is repeated in the same way for the other outcomes of interest. Therefore, the patients were not censored at the first outcome of interest and outcomes on treatment after the first is also taken in to account. Only first-time events of the same type are considered.
- End of observation time (data lock point for the database at 31st October 2017)
- Treatment discontinuation
- Treatment switching patients who switched will be censored at the time of the date of a filled prescription from a pharmacy of the new drug.

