Annex 3: Additional information

Table 1. ATC codes for anticoagulant drugs

Class	Drug name	ATC code
1. Parenteral anticoagulants	Heparin	B01AB01
	Enoxaparin	B01AB05
	Dalteparin	B01AB04
	Nadroparin	B01AB06
	Tinzaparin	B01AB10
	Reviparin	B01AB08
	Parnaparin	B01AB07
	Bemiparin	B01AB12
	Fondaparinux	B01AX05
	Danaparoid	B01AB09
	Bivalirudin	B01AE06
	Argatroban	B01AE03
	2. Vitamin K antagonists	Warfarin
Phenprocoumon		B01AA04
Acenocoumarol		B01AA07
Dicoumarol		B01AA01
Tioclomarol		B01AA11
Ethyl biscoumacetate		B01AA08
Fluindione		B01AA12
Phenindione		B01AA02
Chlorindione		B01AA09
Diphenadione		B01AA10
3. Non-vitamin K oral anticoagulants (NOACs)	Rivaroxaban (Xarelto)	B01AF01
	Dabigatran (Pradaxa)	B01AE07
	Apixaban (Eliquis)	B01AF02
	Edoxaban (Savaysa/Lixiana)	B01AF03

Tabel 2. ICD-10 codes used to define disease conditions

Condition	ICD-10 or Swedish procedure code beginning with
Intracranial bleeding	I60-62, S064, S065, S066
Gastrointestinal bleeding	I850, I983, K226, K250, K252, K254, K256, K260, K262, K264, K266, K270, K272, K274, K276, K280, K284, K286, K290, K625, K661, K920, K921, K922
Urogenital bleeding	N02, R319, N95
Other bleeding	H431, R04, R58, D629, procedure code DR029
Anaemia	D50-64
Coagulation or platelet defect	D65-69
Ischaemic stroke	I63
Heart failure	I50, I110, I130, I132, I255, K761, I42-43
Unspecified stroke	I64
TIA	G45
Peripheral systemic emboli	I74
Thromboembolism (composite)	I63-64, G45, I74
Pulmonary embolism	I26
Deep venous thrombosis	I801-802
Venous thromboembolism (composite)	I26, I801-802
Myocardial infarction	I21, I252
Ischaemic heart disease	I20-25

“Swedish alcohol index” : will be used with ICD-10 codes: E244, F10, G312, G621, G721, I426, K292, K70, K860, O354, P043, Q860, T51, Y90-91, Z502, Z71

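### The Annex 3 code list for the bleeding outcome omits K282 and any prostate haemorrhage code and includes a category that cannot occur in men, so bleeding can only be undercounted, by an amount the protocol does not allow one to size

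*Protocol*

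**What the plan says.** Section 9.3.3 names "Bleeding events leading to hospitalisation" as the second outcome in men with prostate cancer. It serves a primary objective (section 8.1): "To estimate the incidence rates of post-VTE bleeding events leading to hospitalization, and mortality by anticoagulation treatment". This is Objective 7 in the abstract and in section 9.8.

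Section 9.4.1 gives the components: "major bleeding event i.e. intracranial, gastrointestinal, urogenital bleeding, or other bleeding leading to hospitalisation". Section 9.3.1 also lists "urogenital bleeding" among the prior events to be recorded at baseline by ICD code, next to intracranial and gastrointestinal bleeding.

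Annex 3 Table 2 is the only diagnosis code list for these conditions in the protocol. Its column heading says that codes are matched by how they begin. The relevant rows are:

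- **Gastrointestinal bleeding**, peptic ulcer part: "K250, K252, K254, K256, K260, K262, K264, K266, K270, K272, K274, K276", followed by "K280, K284, K286, K290".
- **Urogenital bleeding**: N02, R319 and N95, and nothing else.
- **Other bleeding**: "H431, R04, R58, D629, procedure code DR029".

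**The concern.** The list departs from its own pattern in one row and from the study population in another. Three ulcer families carry four bleeding subcodes each and the fourth carries three, with no reason given. The urogenital row has a female category as its only genital entry, in a study of men with prostate cancer, and has no entry for bleeding from the prostate.

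Section 9.8 plans no comparison between anticoagulants, so the absolute bleeding rates by treatment are themselves the result. A bleed that the list does not recognise is left out of the numerator, and the man's follow-up continues past it. The same gap would leave some men recorded at baseline without a bleeding history that they have.

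**Working it through.** The protocol gives no expected bleeding rate, so there is no stated figure to reproduce. The check is of the code list itself.

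**Step 1: completeness of the ulcer families in the gastrointestinal row.**

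| Family | Subcodes listed | Of 0, 2, 4, 6 | Missing |
|---|---|---|---|
| K25 | 0, 2, 4, 6 | 4 of 4 | none |
| K26 | 0, 2, 4, 6 | 4 of 4 | none |
| K27 | 0, 2, 4, 6 | 4 of 4 | none |
| K28 | 0, 4, 6 | 3 of 4 | K282 |

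This gap shows from the table alone.

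**Step 2: prefix matching against all four bleeding rows** (intracranial, gastrointestinal, urogenital, other).

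| Code | Caught by a listed prefix? |
|---|---|
| K282 | no |
| N42, including N421 (prostate haemorrhage) | no |
| N50, including N501 (vascular disorders of male genital organs) | no |
| N02, R319 (haematuria) | yes |
| R58 | yes |
| N95 (menopausal disorders) | yes, but cannot occur in men |

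The meanings of N95, N421 and N501 are the standard ones in the classification that the protocol uses. The protocol does not print them.

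**Step 3: direction.** N95 adds no events and loses none. An admission carrying K282 or N421 is lost only if it carries no other listed bleeding code. Under section 9.8 person-time runs to the event, death or end of follow-up, so a lost event lowers the numerator and lengthens the denominator. If the man later has a listed bleed, the event is counted late, and the extra person-time still lowers the rate. Neither omission can raise a rate.

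**Step 4: size, by assumption only.** Let *s* be the share of true bleeding events recorded only under an omitted code and not followed by a listed bleed in the same man. Then observed count / true count = 1 − *s*.

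| Assumed *s* | 1 − *s* |
|---|---|
| 0.1% | 0.999 |
| 1% | 0.99 |
| 5% | 0.95 |
| 10% | 0.90 |

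The ratio of rates is slightly lower still because of the added person-time. Nothing in the protocol says where in this range *s* lies. A given share within the urogenital component alone is a smaller share of the four-part outcome.

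**Step 5: after correction.** With K282 added, K28 has 4 of 4 subcodes, like the other three families. With N421 in place of N95, every urogenital code can occur in the study population.

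**The case against.** The strongest reply is that little is lost. Prostatic bleeding may often be recorded as haematuria, which N02 and R319 cover, and R58, D629 and procedure code DR029 in the other-bleeding row may pick up further cases. The protocol does not show how often Swedish admissions carry a prostate haemorrhage code alone. K282 is one subcode of one ulcer family. The same list applies to every treatment group, and no comparison between groups is planned. This all stands, and it limits the size of the problem. It does not remove it, since the absolute rates are what the study reports.

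It can also be said that the protocol never states outright that these rows define the outcome: section 9.5 refers to Annex 3 for the drug codes and the venous thromboembolism codes. That is true, but the row names match the components in section 9.4.1, Annex 1 lists no stand-alone documents, and no other bleeding code list is given. The inference is reasonable.

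Three stronger readings are tempting but not supported:

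- **N95 causes missed bleeds.** It does not. It is inert in men and shows only that the row was not adapted to them.
- **Every admission for prostate haemorrhage is missed.** Only those with no other listed bleeding code are missed.
- **The understatement can be given as a percentage.** The documents contain no figure from which to derive one.

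**Conclusion.** Annex 3 Table 2 has definite but limited errors. The K282 omission follows from the table's own pattern. The urogenital point rests on the ordinary meaning of the ICD-10 codes: one listed category cannot occur in men, and prostate haemorrhage has no code, so only haematuria can qualify.

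Used as written, the list would fail to count admissions recorded only under K282 or a prostate haemorrhage code. The effect on the Objective 7 rates and on baseline bleeding history can only be downward. Its size is unknown and may be small. The conclusion assumes that the Annex 3 rows are the operational definition of the bleeding components, as their names indicate. It is worth correcting because the outcome serves a primary objective and the correction is cheap, not because a large bias has been shown.

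**What to change.** In Annex 3 Table 2:

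1. Add K282 to gastrointestinal bleeding.
2. Delete N95 from urogenital bleeding and put N421 in its place.
3. State that the revised rows define both the bleeding outcome of section 9.3.3 and the baseline bleeding history of section 9.3.1, and apply them to both.
4. Keep N501 out of the main definition. It also covers non-bleeding disorders, so counting it would exchange possible undercounting for false positives. Use it only in a sensitivity analysis with its events tabulated separately.

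The cost is two codes added, one removed and one small extra table. No new data are needed. Made before programming, the change costs almost nothing; made afterwards, the bleeding analyses and the baseline tables have to be rerun.
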